2 ANALYSIS PLAN

All endpoints will be analyzed descriptively within each of the three age groups. N (non-missing sample size), mean, standard deviation, median, minimum, and maximum will be presented for continuous variables. Count and percentage (based on the non-missing sample size) will be presented for discrete variables.

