9. After 5 minutes, a confirmatory plasma glucose measurement will be performed.
  - a. If plasma glucose remains  $< 80$  mg/dL, collect a second baseline PK blood sample, and begin administration of the study drug (see Section 9.3.2).
  - b. If plasma glucose has risen to  $\geq 80$  mg/dL, return to step 7b and repeat the process.
10. Following study dosing, plasma glucose will be measured every  $5 \pm 2$  minutes until 90 minutes post-dosing.

11. Additional blood samples will be collected at 10, 20, 30, 45, 60, 90, 120, and 180 minutes post-dosing, with  $\pm 5$  minutes per collection, and processed and stored at  $-80 \pm 20$  C for determination of plasma glucagon levels.
12. After completing all collections and procedures at 180 minutes post-dosing, the subject will be given a meal as per the standard practice at each site, and their usual dose of insulin. The subject can then leave the clinic after plasma glucose is confirmed to be between 70 and 180 mg/dL.
13. Local tolerability will be assessed as follows:
  - a. Subjects will complete age-appropriate questionnaires regarding injection site discomfort ([Appendix 1](#)) at  $10 \pm 5$  and  $30 \pm 5$  minutes post-dosing, and again at  $180 \pm 5$  minutes post-dosing if the FPS score reported at 30 minutes is  $> 0$ .
  - b. An investigator will use the modified Draize scales ([Appendix 2](#)) to assess erythema and edema formation at the injection site at  $10 \pm 5$  and  $30 \pm 5$  minutes following administration. Any injection site with a score  $> 0$  for either erythema or edema at 30 minutes post-dosing will be re-evaluated for both at  $180 \pm 5$  minutes post-dosing.
14. Adverse events reported by the subject or observed by an investigator will be recorded in Advantage eClinical and managed as medically appropriate.

If a subject exhibits signs of distress at any time post-dosing or if plasma glucose drops below  $< 70$  mg/dL, glucose tablets may be given at the discretion of the investigator. Signs and symptoms should be monitored and if the subject's condition fails to improve within 15 minutes, additional glucose tablets or other intervention (e.g., IV dextrose) may be given at the discretion of the investigator. Every attempt should be made to complete all remaining safety and efficacy evaluations, to the extent this can be done while safeguarding the subject.

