### Faces Pain Scale – Revised (FPS-R)

*Investigative Site Instructions:* The subject should complete the FPS-R regarding injection site discomfort at both **10±5** minutes and **30±5** minutes following the injection of study drug, and again before the end of the clinic visit if the FPS score at **30±5** minutes is > 0. The subject completes the FPS by choosing the face that corresponds to their current level of pain. The goal is for the subject to report the amount of discomfort, if any, remaining at each time point, as opposed to reporting the transient pain associated with needle insertion.

Show the faces to the subject and provide the following instructions, using the words “hurt” or “pain,” whichever seems right for a particular subject:

**“These faces show how much something can hurt. This face [point to the face on far left] shows no pain. The faces show more and more pain [point to each from left to right] up to this one [point to face on far right] – It shows very much pain. Point to the face that shows how much you hurt right now.”**

Score the chosen face 0, 2, 4, 6, 8 or 10, counting left to right, so 0 = no pain and 10 = very much pain.

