## APPENDIX 2. DRAIZE SCALE

*Study Personnel Instructions:* The modified Draize Scale as shown in the table below will be used for physical examination/rating of abnormalities at the injection site.

The injection site should be examined for formation of both erythema and edema and results recorded in the Case Report Form. Evaluations of the injection site should be performed at 10±5 and 30±5 minutes post-treatment, and again at the end of the treatment visit (i.e., at approximately 180±5 minutes post-dosing) if any scores > 0 were noted at 30-minutes post-dosing.

Erythema Formation		Edema Formation	
Description	Score	Description	Score
No erythema	0	No edema	0
Very slight erythema Barely perceptible	1	Very slight edema Barely perceptible	1
Well defined erythema	2	Well defined edema	2
Moderate erythema	3	Moderate edema Raised approx. 1 mm	3
Severe erythema Beet redness to slight eschar formation	4	Severe edema Raised more than 1 mm and beyond exposure area	4

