Table 14: Severity of adverse events and their relatedness to study by MedDRA® system organ class and preferred term, and treatment dose (continued)**Treatment emergent adverse events (TEAE)**

MedDRA® System Organ Class (SOC)	MedDRA® Preferred Term (PT)	G-Pen™ Dose																			
		0.5 mg (N=X)										1.0 mg (N=X)									
		Severity				Relatedness				Severity				Relatedness				Study Drug		Study Device	
		Mild		Moderate		Severe		Study Drug		Study Device		Study Procedure		Mild		Moderate		Severe		Study Drug	
		n	%	n	%	n	%	n	%	n	%	n	%	n	%	n	%	n	%	n	%
Any SOC	Any PT	xx	xx.x	xx	xx.x	xx	xx.x	xx	xx.x	xx	xx.x	xx	xx.x	xx	xx.x	xx	xx.x	xx	xx.x	xx	xx.x
[SOC 1]	Any PT	xx	xx.x	xx	xx.x	xx	xx.x	xx	xx.x	xx	xx.x	xx	xx.x	xx	xx.x	xx	xx.x	xx	xx.x	xx	xx.x
	[PT 1]	xx	xx.x	xx	xx.x	xx	xx.x	xx	xx.x	xx	xx.x	xx	xx.x	xx	xx.x	xx	xx.x	xx	xx.x	xx	xx.x
	[PT 2]	xx	xx.x	xx	xx.x	xx	xx.x	xx	xx.x	xx	xx.x	xx	xx.x	xx	xx.x	xx	xx.x	xx	xx.x	xx	xx.x
[SOC 2]	Any PT	xx	xx.x	xx	xx.x	xx	xx.x	xx	xx.x	xx	xx.x	xx	xx.x	xx	xx.x	xx	xx.x	xx	xx.x	xx	xx.x
	[PT 1]	xx	xx.x	xx	xx.x	xx	xx.x	xx	xx.x	xx	xx.x	xx	xx.x	xx	xx.x	xx	xx.x	xx	xx.x	xx	xx.x
	[PT 2]	xx	xx.x	xx	xx.x	xx	xx.x	xx	xx.x	xx	xx.x	xx	xx.x	xx	xx.x	xx	xx.x	xx	xx.x	xx	xx.x

¹Note: This table presents number and percentage of subjects. A subject is only counted once per PT and is summarized according to their highest severity and closest relationship. A subject may have multiple PTs.

²Any SAE occurred will be summarized in the footnote.

Listing 2: Abnormality in the physical examination evaluation at screening

Subject ID	Age Group	Physical Exam	Abnormal Finding

Table 15: Vital signs before and after administration of G-Pen™ by age group and by treatment dose for subjects aged 12.0-<18.0**Age Group: 2.0-<6.0 years (N=X)**

	Time					Change from Baseline ^a	
	Baseline	30 minutes	60 minutes	120 minutes	180 minutes	Max Increase	Max Decrease
Heart Rate, beats/min							
N	x	x	x	x	x	x	x
Mean (SD)	xxx.x (xxx.x)	xxx.x (xxx.x)					
Median	xxx	xxx	xxx	xxx	xxx	xxx	xxx
[Min-Max]	[xxx-xxx]	[xxx-xxx]	[xxx-xxx]	[xxx-xxx]	[xxx-xxx]	[xxx-xxx]	[xxx-xxx]
Systolic BP, mmHg							
N	x	x	x	x	x	x	x
Mean (SD)	xxx.x (xxx.x)	xxx.x (xxx.x)					
Median	xxx	xxx	xxx	xxx	xxx	xxx	xxx
[Min-Max]	[xxx-xxx]	[xxx-xxx]	[xxx-xxx]	[xxx-xxx]	[xxx-xxx]	[xxx-xxx]	[xxx-xxx]
Diastolic BP, mmHg							
N	x	x	x	x	x	x	x
Mean (SD)	xxx.x (xxx.x)	xxx.x (xxx.x)					
Median	xxx	xxx	xxx	xxx	xxx	xxx	xxx
[Min-Max]	[xxx-xxx]	[xxx-xxx]	[xxx-xxx]	[xxx-xxx]	[xxx-xxx]	[xxx-xxx]	[xxx-xxx]

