	Baseline	30 minutes	60 minutes	120 minutes	180 minutes	Max Increase	Max Decrease
Heart Rate, beats/min							
N	x	x	x	x	x	x	x
Mean (SD)	xxx.x (xxx.x)	xxx.x (xxx.x)					
Median	xxx	xxx	xxx	xxx	xxx	xxx	xxx
[Min-Max]	[xxx-xxx]	[xxx-xxx]	[xxx-xxx]	[xxx-xxx]	[xxx-xxx]	[xxx-xxx]	[xxx-xxx]
Systolic BP, mmHg							
N	x	x	x	x	x	x	x
Mean (SD)	xxx.x (xxx.x)	xxx.x (xxx.x)					
Median	xxx	xxx	xxx	xxx	xxx	xxx	xxx
[Min-Max]	[xxx-xxx]	[xxx-xxx]	[xxx-xxx]	[xxx-xxx]	[xxx-xxx]	[xxx-xxx]	[xxx-xxx]
Diastolic BP, mmHg							
N	x	x	x	x	x	x	x
Mean (SD)	xxx.x (xxx.x)	xxx.x (xxx.x)					
Median	xxx	xxx	xxx	xxx	xxx	xxx	xxx
[Min-Max]	[xxx-xxx]	[xxx-xxx]	[xxx-xxx]	[xxx-xxx]	[xxx-xxx]	[xxx-xxx]	[xxx-xxx]

SD= standard deviation; BP= blood pressure.

^a Positive value indicates an increase from baseline and negative value indicates a decrease.

Figure 4: Vital signs before and after administration of G-Pen™ by age group and by treatment dose for subjects aged 12.0-<18.0

BP= blood pressure.

Table 16: Incidence of any injection site discomfort by age group and by treatment dose for subjects aged 12.0-<18.0

Age Group	G-Pen™ Dose	Incidence of Any Injection Site Discomfort ^a					
		10 minutes		30 minutes		180 minutes	
		n	%	n	%	n	%
2.0-<6.0 years (N=X)	0.5 mg	x	x.x	x	x.x	x	x.x
6.0-<12.0 years (N=X)	0.5 mg	x	x.x	x	x.x	x	x.x
12.0-<18.0 years (N=X)	1.0 mg	x	x.x	x	x.x	x	x.x
12.0-<18.0 years (N=X)	0.5 mg	x	x.x	x	x.x	x	x.x

^a Any injection site discomfort is defined as Faces Pain Scale – Revised (FPS-R) score >0.

Table 17: Incidence of erythema after administration of G-Pen™ by age group and by treatment dose for subjects aged 12.0-<18.0

Age Group	G-Pen™ Dose	Incidence of Erythema ^a					
		10 minutes		30 minutes		180 minutes	
		n	%	n	%	n	%
2.0-<6.0 years (N=X)	0.5 mg	x	x.x	x	x.x	x	x.x
6.0-<12.0 years (N=X)	0.5 mg	x	x.x	x	x.x	x	x.x
12.0-<18.0 years (N=X)	1.0 mg	x	x.x	x	x.x	x	x.x
12.0-<18.0 years (N=X)	0.5 mg	x	x.x	x	x.x	x	x.x

^a Erythema formation is defined as Modified Draize Scale score for erythema >0.

Table 18: Incidence of edema after administration of G-Pen™ by age group and by treatment dose for subjects aged 12.0-<18.0

Age Group	G-Pen™ Dose	Incidence of Edema ^a					
		10 minutes		30 minutes		180 minutes	
		n	%	n	%	n	%
2.0-<6.0 years (N=X)	0.5 mg	x	x.x	x	x.x	x	x.x
6.0-<12.0 years (N=X)	0.5 mg	x	x.x	x	x.x	x	x.x
12.0-<18.0 years (N=X)	1.0 mg	x	x.x	x	x.x	x	x.x
12.0-<18.0 years (N=X)	0.5 mg	x	x.x	x	x.x	x	x.x

^a Edema formation is defined as Modified Draize Scale score for edema >0.

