
Figure 5: Local tolerability by age group and by treatment dose for subjects aged 12.0-<18.0

[figure not shown]

Table 19: Time of onset and duration of discomfort and discomfort description by age group and by treatment dose for subjects aged 12.0-<18.0				
	2.0-<6.0 years (N=X^{a,b})	6.0-<12.0 years (N=X^a)	12.0-<18.0 years with 1.0 mg (N=X^a)	12.0-<18.0 years with 0.5 mg (N=X^a)
Time of Onset, minute				
N	x	x	x	x
Mean (SD)	xx.x (xx.x)	xx.x (xx.x)	xx.x (xx.x)	xx.x (xx.x)
Median	xx	xx	xx	xx
[Min-Max]	[xx-xx]	[xx-xx]	[xx-xx]	[xx-xx]
Duration – n (%)				
< 1 minute	x (x.x)	x (x.x)	x (x.x)	x (x.x)
1-2 minutes	x (x.x)	x (x.x)	x (x.x)	x (x.x)
3-5 minutes	x (x.x)	x (x.x)	x (x.x)	x (x.x)
6-9 minutes	x (x.x)	x (x.x)	x (x.x)	x (x.x)
10-15 minutes	x (x.x)	x (x.x)	x (x.x)	x (x.x)
16-30 minutes	x (x.x)	x (x.x)	x (x.x)	x (x.x)
30-120 minutes	x (x.x)	x (x.x)	x (x.x)	x (x.x)
121-180 minutes	x (x.x)	x (x.x)	x (x.x)	x (x.x)
Discomfort Description ^c				
Pain (e.g. throbbing, soreness, muscle ache) – n (%)	x (x.x)	x (x.x)	x (x.x)	x (x.x)
Itching – n (%)	x (x.x)	x (x.x)	x (x.x)	x (x.x)
Tingling, twitching, or numbness – n (%)	x (x.x)	x (x.x)	x (x.x)	x (x.x)
Irritation (e.g. burning, stinging) – n (%)	x (x.x)	x (x.x)	x (x.x)	x (x.x)

^aOnly those who reported having at least one discomfort post-injection are included in the table.

^bX subjects are not applicable because they are too young for comprehension.

^cA subject may report more than one discomfort.

Listing 3: Pregnancies and outcomes

Subject ID	Age group	G-Pen™ dose	Number of Embryos, Fetuses, and/or Infants	Outcome	Congenital Anomaly?	Gestational Age (weeks and days)	Gender	Weight (lbs)	Length (in)	Head Circumference (cm)

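### Read literally, the SAP's non-missing percentage base makes 180-minute discomfort, erythema and edema incidence a persistence rate among the subjects reassessed (minor)

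*SAP*

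**What the plan says.** **Percentage rule.** SAP 2 states: "Count and percentage (based on the non-missing sample size) will be presented for discrete variables". It makes no exception for assessments that are conditional by design. SAP 2.5.4 (Local Tolerability) does not mention the condition, and SAP 3.3 (Missing Data) deals with glucose data for the efficacy analyses only.

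**FPS-R at 180 minutes.** Protocol 10.2.1, step 13a, asks for the repeat "minutes post-dosing if the FPS score reported at 30 minutes is" above 0. Appendix 1 agrees: "and again before the end of the clinic visit if the FPS score at" 30 minutes is above 0.

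**Draize at 180 minutes.** Protocol 10.2.1, step 13b, says a site scoring above 0 "for either erythema or edema at 30 minutes post-dosing will be re-evaluated for both" at 180 minutes. Appendix 2 repeats the check "if any scores > 0 were noted at 30-minutes post-dosing". Protocol 7.1 lists the 10-, 30- and 180-minute Draize checks with no condition.

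**Table shells.** Mock-up Table 16 ("Incidence of any injection site discomfort") and Tables 17 and 18 (erythema, edema) give n and % at 10, 30 and 180 minutes, with one N per age and dose row. Their footnotes define the event as a score above 0 but give no denominator. SAP 2.5.4 cites these outputs as Tables 15-17.

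**The concern.** The subjects scored at 180 minutes are selected on the outcome itself: for FPS-R, only those positive at 30 minutes are asked again. If the others count as missing, the 180-minute percentage describes how often an existing reaction persisted. The 10- and 30-minute percentages describe how common a reaction was in the group. All three would stand in one row under the word incidence.

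A reader following the row could then see discomfort apparently becoming more common between 30 and 180 minutes while the number affected had fallen. Tolerability is a secondary objective and these tables summarise it, so the column should mean what its heading says. The primary glucose analysis is not touched.

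**Working it through.** The documents state no 180-minute incidence and no positivity rates, so there is no figure to reproduce. All counts below are assumed, except the group sizes.

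**Inputs**
- N = subjects in a row assessed at 30 minutes. The evaluable target is 6 per age group (protocol synopsis, SAP 1.3). Up to 8 (protocol synopsis) or 12 (SAP 1.3) may be treated per group.
- k = subjects scored at 180 minutes, assumed 0 to N.
- m = subjects scoring above 0 at 180 minutes, assumed 0 to k.

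**Two denominators**
- SAP 2 rule, with scores not called for treated as missing: m/k.
- All N, with subjects not reassessed taken as 0: m/N.
- For m of at least 1, the ratio is (m/k)/(m/N) = N/k.

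| k, at N = 6 | 1 | 2 | 3 | 4 | 5 | 6 |
|---|---|---|---|---|---|---|
| N/k | 6 | 3 | 2 | 1.5 | 1.2 | 1 |

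**Example, FPS-R, N = 6.** Two subjects are positive at 30 minutes: 2/6 = 33.3%. Both are reassessed and one is still positive. The rule prints 1/2 = 50.0%; the fixed base gives 1/6 = 16.7%. A fall is shown as a rise. With k = 2 and m = 1 in a larger row, the rule still prints 50.0%, against 1/8 = 12.5% or 1/12 = 8.3%.

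**When FPS-R appears to rise.** With no missed reassessment, the 30-minute percentage is k/N. Since m cannot exceed k, m/N cannot exceed k/N. The printed m/k exceeds k/N when m > k²/N. At N = 6:

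| k | 30-minute % | Smallest m giving a rise | Printed 180-minute % |
|---|---|---|---|
| 1 | 16.7 | 1 | 100 |
| 2 | 33.3 | 1 | 50 |
| 3 | 50 | 2 | 66.7 |
| 4 | 66.7 | 3 | 75 |
| 5 | 83.3 | 5 | 100 |
| 6 | 100 | none | – |

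**Draize under 10.2.1 and Appendix 2.** Here k counts sites positive on either sign, and the same k serves Tables 17 and 18. At N = 6, one erythema-only and one edema-only site give k = 2. If the erythema persists, the rule prints 1/2 = 50.0% against 1/6 = 16.7%. If protocol 7.1 is followed, every site is scored, so k = N and the ratio is 1.

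**Edge cases.** If k = 0 the rule gives 0/0, where the fixed base gives 0/N = 0%. If k = N, or if m = 0 with k of at least 1, the two agree.

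**Required scores that are missing.** Suppose N = 6, three are positive at 30 minutes, one of them misses the 180-minute score, and one of the other two is still positive. The rule gives 1/2 = 50.0%. Excluding the missed subject gives 1/(6 − 1) = 20.0%. Keeping that subject as a non-event gives 1/6 = 16.7%, and as an event 2/6 = 33.3%. The treatment of such subjects therefore has to be stated, and their number reported.

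**The case against.** **The rule and the shells do not contradict each other.** A reader might infer a conflict because Tables 16-18 print one N per row while the vital-signs shell ("Vital signs before and after administration of G-Pen™ by age group and by treatment dose for subjects aged 12.0-<18.0") prints an N at each time point. The documents do not support this. SAP 2 prescribes N lines for continuous variables and only counts and percentages for discrete ones, and Table 6 follows the same layout. No shell says that the percentage is n divided by the row N. Nor do protocol 10.3 (who enters the safety analysis) or 13.3.1 (adverse events) set a time-point denominator. This objection stands: the shells fail to correct the rule, but they do not oppose it.

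**Inflation is not certain.** It requires an assessment the protocol did not ask for to be read as missing. Counting such subjects as negative is also a natural reading, and then there is no inflation. This stands too; the defect is that nothing in the SAP chooses between the readings.

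**A careful reader can recover the base.** For FPS-R, k equals the 30-minute count in the same row if no reassessment was missed. Table 19 also reports duration, with a 121-180 minute category. This limits the harm for FPS-R. It helps less for Draize under 10.2.1, where k is the union of two signs reported in separate tables and their overlap is not shown.

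**The tables are small and descriptive.** No test or decision depends on them. This stands and sets the severity.

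**Conclusion.** The point holds at minor severity. Applied literally, SAP 2 gives m/k at 180 minutes, which is persistence among those reassessed, under a heading of incidence. Relative to a base of everyone assessed at 30 minutes, the printed figure is larger by N/k: from 1 to 6 at N = 6, and undefined when k = 0.

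This rests on three conditions:
- Scores not called for are treated as missing.
- Subjects at 0 at 30 minutes are taken to be 0 at 180 minutes, which the schedule does not observe.
- For Draize, the conditional text of protocol 10.2.1 and Appendix 2 is followed and not protocol 7.1. FPS-R has no such contrary text.

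The actual size cannot be known because the documents give no positivity rates. The effect is confined to one column in three descriptive tables with n printed. A reader might go further and infer that reported tolerability will be materially wrong, or that the trial's conclusions are at risk. The documents support neither.

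**What to change.** **SAP.** In 2.5.4 and the footnotes of mock-up Tables 16-18, choose one of two options.

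1. Define the 180-minute denominator as all dosed subjects assessed at 30 minutes, excluding those whose required 180-minute score is missing, and report the number excluded. Count subjects not reassessed because of a 30-minute score of 0 as 0. State that this assumes they stayed clear, and that reactions first appearing after 30 minutes are not captured.
2. Relabel the column *persistence among those reassessed* and print k beside it.

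Either option costs a short addition to 2.5.4 and three footnotes, with no new data. The price of option 1 is the untested assumption about subjects not reassessed. The price of option 2 is that the column is no longer a group incidence.

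**Protocol.** Reconcile 7.1 with 10.2.1 and Appendix 2 on whether the 180-minute Draize check is conditional. Under protocol 18.1 a protocol modification needs IRB approval before use, so this wording can wait for the next amendment. The SAP text need not wait.

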2.1 Analysis Population and Protocol Compliance

The study flow chart displays the enrollment process from screened subjects to the analysis population (Figure 1). Reasons for screening failures will be summarized (Table 1). Subject disposition will be summarized by age group (Table 2). Reasons for discontinued treatment and early termination (Table 3), as well as completion rate for the post-dosing phone call follow-up (Table 4), will be additionally summarized by age group. Protocol deviations will be summarized by age group (Table 5), and a full listing of all deviations will be summarized by site (Listing 1).

2.2 Demographic and Baseline Clinical Characteristics

Summaries of age, gender, ethnicity, race, clinical sites, and baseline clinical characteristics will be presented by age group (Table 6). Ethnicity is categorized as Hispanic or Latino, or not Hispanic or Latino.

2.3 Efficacy Analysis

2.3.1 Efficacy Primary Endpoint

The primary endpoint is the change in plasma glucose at 30 minutes post-dosing from baseline, which is defined as the average of the two plasma glucose measurements (i.e., -5 and 0 minutes) completed immediately prior to dosing. In addition to the descriptive summary, a simple *t*-test will be used to test whether there is a significant change in glucose from baseline to 30 minutes within each of the three age groups (Table 7). All three tests are 2-sided with α -level of 0.05.

2.4 Pharmacokinetic and Pharmacodynamic Analyses

The PK endpoints will be derived from the individual serum glucagon profiles. The PD endpoints will be derived from the individual glucose profiles.

2.4.1 Pharmacokinetic Endpoints

The data for each age group and the overall population will be analyzed descriptively, including serum glucagon AUC_{0-180m} , C_{max} and T_{max} . The analysis will be conducted by IMD (See Appendix II).

2.4.2 Pharmacodynamic Endpoints

In the 12.0-<18.0 year-old age group, the plasma glucose change from baseline to 30 minutes after administration of G-Pen™ at a dose of 0.5 mg will be evaluated using the same approach described in Section 2.3.1 (Table 8).

Time for plasma glucose to increase by ≥ 25 mg/dL from baseline, maximum glucose concentration (C_{max}) between 0 and 90 min, the time to maximum concentration (T_{max}) will be directly obtained from the observed glucose concentration-time profile. If two identical values are recorded for C_{max} , the first one will be used for T_{max} . The area under the curve from 0 to 90 min (AUC_{0-90m}) of glucose will be calculated as the sum of areas of trapezoids, which are composed of adjacent glucose values. The following rules will be considered:

1. If there are missing data points before the last observed value, they will not be imputed.
2. If there are missing data points after the last observed value, they will be extrapolated using the last two data points.

Baseline-adjusted AUC_{0-90m} with negative values set at 0 will also be calculated. All PD endpoints will be analyzed descriptively for each age group (Table 9) and by treatment dose for subjects aged 12.0-<18.0 (Table 10). Actual time instead of protocol time will be used for calculating the time for plasma glucose to increase by ≥ 25 mg/dL from baseline, T_{max} , AUC_{0-90m} , and baseline-adjusted AUC_{0-90m} . In addition, plasma glucose concentration-time profile by age group (Figure 2 and Table 11) and by treatment dose for subjects aged 12.0-<18.0 (Figure 3 and Table 11) will be presented.

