3.2 Analysis Cohort

The efficacy and PD analyses will include all participants who completed the dosing visit with the following exceptions:

- Dosing visits during which a glucose-elevating intervention is given after administration of G-Pen™ will be included in the analysis, but the glucose values after the additional intervention post-dosing will be censored.
- For the efficacy analysis, if the additional intervention is given before 30 minutes post-dosing, then the 30-minute post-dosing measurement will be replaced with the last glucose measurement prior to the intervention.
- For the PD analysis., if the additional intervention is given shortly after administration of G-Pen™ (i.e., more than half of the glucose values is censored), the subject will be excluded from the analysis.

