3.3 Missing Data

For the efficacy analyses, last observation carried forward (LOCF) will be applied for subjects who drop out before 30 minutes post-dosing or who otherwise have missing primary endpoint data (e.g. missed blood draws). Baseline glucose is calculated as the mean of the initial glucose measurement <80 mg/dL and a second confirmatory measurement prior to dosing. If either one measurement is missing, then the available one will be used as the baseline glucose value. If both measurements are missing, the patient will not be included in the efficacy analyses, given there is no confirmation measurements the subject reached a blood glucose value of <80 mg/dL prior to receiving the glucagon injection. The proportion of non-analyzable subjects is expected to be low and will be monitored by the Clinical Research Associate (CRA) (or designee) throughout the trial.

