Clinical Site – n (%)			
Barbara Davis Center for Childhood Diabetes	x (x.x)	x (x.x)	x (x.x)
Women & Children's Hospital of Buffalo	x (x.x)	x (x.x)	x (x.x)
University of Florida Diabetes Institute	x (x.x)	x (x.x)	x (x.x)
Riley Hospital for Children at IU Health	x (x.x)	x (x.x)	x (x.x)
University of Iowa Hospitals and Clinics	x (x.x)	x (x.x)	x (x.x)
Nemours Children's Clinic	x (x.x)	x (x.x)	x (x.x)
Lucile Packard Children's Hospital at Stanford	x (x.x)	x (x.x)	x (x.x)
Yale University School of Medicine	x (x.x)	x (x.x)	x (x.x)

^a Calculated as weight in kilograms divided by height in meters squared.
 SD=standard deviation.

Efficacy Data

Table 7: Plasma glucose before and 30 minutes after administration of G-Pen™ by age group				
Age Group	Plasma Glucose (mg/dL) Mean (SD), median, [min – max]			P-value^a
	Baseline	30 minutes	Change	
2.0-<6.0 years (N=X)	xx.x (xx.x), xx, [xx-xx]	xxx.x (xxx.x), xxx, [xxx-xxx]	xxx.x (xxx.x), xxx, [xxx-xxx]	x.XXX
6.0-<12.0 years (N=X)	xx.x (xx.x), xx, [xx-xx]	xxx.x (xxx.x), xxx, [xxx-xxx]	xxx.x (xxx.x), xxx, [xxx-xxx]	x.XXX
12.0-<18.0 years (N=X)	xx.x (xx.x), xx, [xx-xx]	xxx.x (xxx.x), xxx, [xxx-xxx]	xxx.x (xxx.x), xxx, [xxx-xxx]	x.XXX

^a P-value computed using *t*-test for testing whether the change in glucose from baseline to 30 minutes is zero.

SD= standard deviation.

Table 8: Plasma glucose before and 30 minutes after administration of G-Pen™ in the 12.0-<18.0 year-old age group at a dose of 0.5 mg

Age Group	Plasma Glucose (mg/dL) Mean (SD), median, [min – max]			P-value^a
	Baseline	30 minutes	Change	
12.0-<18.0 years (N=X)	xx.x (xx.x), xx, [xx-xx]	xxx.x (xxx.x), xxx, [xxx-xxx]	xxx.x (xxx.x), xxx, [xxx-xxx]	x.xxx

^a P-value computed using t-test for testing whether the change in glucose from baseline to 30 minutes is zero.

SD= standard deviation.

Table 9: Plasma glucose AUC_{0-90m}, C_{max}, T_{max}, and time to increase by ≥25 mg/dL from baseline by age group

Age Group	G-Pen™ Dose	Summary Statistics	C _{max} (mg/dL)	T _{max} (min)	AUC _{0-90m} (min*mg/dL)	Baseline-adjusted AUC _{0-90m} (min*mg/dL)	Time to increase by ≥25 mg/dL from baseline
2.0-<6.0 years	0.5 mg	N	x	x	x	x	x
		Mean (SD)	xxx.x (xxx.x)	xx.x (xx.x)	xxx.x (xxx.x)	xxx.x (xxx.x)	xx.x (xx.x)
		Median	xxx	xx	xxx	xxx	xx
		[Min-Max]	[xxx-xxx]	[xx-xx]	[xxx-xxx]	[xxx-xxx]	[xx-xx]
6.0-<12.0 years	0.5 mg	N	x	x	x	x	x
		Mean (SD)	xxx.x (xxx.x)	xx.x (xx.x)	xxx.x (xxx.x)	xxx.x (xxx.x)	xx.x (xx.x)
		Median	xxx	xx	xxx	xxx	xx

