		[Min-Max]	[xxx-xxx]	[xx-xx]	[xxx-xxx]	[xxx-xxx]	[xx-xx]
12.0-<18.0 years	1.0 mg	N	x	x	x	x	x
		Mean (SD)	xxx.x (xxx.x)	xx.x (xx.x)	xxx.x (xxx.x)	xxx.x (xxx.x)	xx.x (xx.x)
		Median	xxx	xx	xxx	xxx	xx
		[Min-Max]	[xxx-xxx]	[xx-xx]	[xxx-xxx]	[xxx-xxx]	[xx-xx]

AUC= area under the curve; C_{max}= maximum plasma concentration; T_{max}= time to maximum plasma concentration; SD= standard deviation.

Table 10: Plasma glucose AUC_{0-90m}, C_{max}, T_{max}, and time to increase by ≥ 25 mg/dL from baseline by treatment dose for subjects aged 12.0-<18.0

G-Pen™ Dose	Summary Statistics	C _{max} (mg/dL)	T _{max} (min)	AUC _{0-90m} (min*mg/dL)	Baseline-adjusted AUC _{0-90m} (min*mg/dL)	Time to increase by ≥ 25 mg/dL from baseline
1.0 mg	N	x	x	x	x	x
	Mean (SD)	xxx.x (xxx.x)	xx.x (xx.x)	xxx.x (xxx.x)	xxx.x (xxx.x)	xx.x (xx.x)
	Median	xxx	xx	xxx	xxx	xx
	[Min-Max]	[xxx-xxx]	[xx-xx]	[xxx-xxx]	[xxx-xxx]	[xx-xx]
0.5 mg	N	x	x	x	x	x
	Mean (SD)	xxx.x (xxx.x)	xx.x (xx.x)	xxx.x (xxx.x)	xxx.x (xxx.x)	xx.x (xx.x)
	Median	xxx	xx	xxx	xxx	xx
	[Min-Max]	[xxx-xxx]	[xx-xx]	[xxx-xxx]	[xxx-xxx]	[xx-xx]

AUC= area under the curve; C_{max}= maximum plasma concentration; T_{max}= time to maximum plasma concentration; SD= standard deviation.

[figure not shown]
Figure 2: Plasma glucose over time by age group

[figure not shown]
Figure 3: Plasma glucose over time by treatment dose for subjects aged 12.0-<18.0

Table 11: Plasma glucose over time by age group and by treatment dose for subjects aged 12.0-<18.0

Plasma Glucose, mg/dL Mean (SD)		Time (min)																			
Age Group	G-Pen™ Dose	-5	0	5	10	15	20	25	30	35	40	45	50	55	60	65	70	75	80	85	90
2.0-<6.0 years (N=X)	0.5 mg	xx.x (xx.x)	xx.x (xx.x)	xxx.x (xxx.x)																	
6.0-<12.0 years (N=X)	0.5 mg	xx.x (xx.x)	xx.x (xx.x)	xxx.x (xxx.x)																	
12.0-<18.0 years (N=X)	1.0 mg	xx.x (xx.x)	xx.x (xx.x)	xxx.x (xxx.x)																	
12.0-<18.0 years (N=X)	0.5 mg	xx.x (xx.x)	xx.x (xx.x)	xxx.x (xxx.x)																	

SD= standard deviation.

Safety Data

Table 12: Number and percentage of subjects experiencing adverse events by MedDRA® system organ class and preferred term, and treatment dose						
Non-treatment emergent adverse events (non-TEAE)						
MedDRA® System Organ Class (SOC)	MedDRA® Preferred Term (PT)	G-Pen™ Dose				
		0.5 mg (N=X)		1.0 mg (N=X)		
		n	%	n	%	
Any SOC	Any PT	xx	x.x	x	x.x	
[SOC 1]	Any PT	xx	x.x	x	x.x	
	[PT 1]	xx	x.x	x	x.x	
	[PT 2]	xx	x.x	x	x.x	
[SOC 2]	Any PT	xx	x.x	x	x.x	
	[PT 1]	xx	x.x	x	x.x	

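### Time to a 25 mg/dL glucose rise has no rule for subjects who never reach it, and the half-censored exclusion can discard a rise already observed

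*SAP*

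**What the plan says.** Time to a rise of at least 25 mg/dL is a named secondary endpoint (Protocol 5.3.2; SAP 1.2.2). Under SAP 2.4.2 it "will be directly obtained from the observed glucose concentration-time profile". For summaries, SAP 2 states: "N (non-missing sample size), mean, standard deviation, median, minimum, and maximum will be presented for continuous variables". The table shells titled "and time to increase by ≥25 mg/dL from baseline by age group" (Table 9) and "and time to increase by ≥ 25 mg/dL from baseline by treatment dose" (Table 10) give only N, mean (SD), median and range in this column. They have no row for the number reaching the rise and none for censored subjects.

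Two rules elsewhere deal with missing glucose values. SAP 3.3 begins "For the efficacy analyses, last observation carried forward (LOCF) will be applied", so it does not extend to the pharmacodynamic endpoints. SAP 2.4.2 also extrapolates points missing after the last observed value; this rule is listed directly after the AUC definition.

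On interventions, SAP 3.2 says that a visit with a glucose-elevating intervention after dosing "will be included in the analysis, but the glucose values after the additional intervention post-dosing will be censored". For the pharmacodynamic analysis it adds an exclusion when the intervention comes early ("more than half of the glucose values is censored), the subject will be excluded from the analysis"). It makes no exception for an endpoint reached before the intervention.

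**The concern.** A subject who never rises by 25 mg/dL is the least favourable result this endpoint can produce, yet as written that subject contributes nothing to the mean or median. More failures then make the surviving summary look faster. Groups are planned at about six, so one or two such subjects matter. Table 10 sets the 1.0 mg and 0.5 mg doses side by side in adolescents, and the dose with more non-reachers would be flattered more.

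The exclusion in SAP 3.2 works differently. It can remove a subject whose time is already known, and it can also remove a subject treated early without any rise, who would otherwise count as a failure.

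The Protocol synopsis expects a rise of at least 25 mg/dL within 30 minutes in every subject, but no planned table counts how many achieve it. The minimum change in the shell headed "Table 7: Plasma glucose before and 30 minutes after administration" can show whether everyone was at or above 25 mg/dL at the 30-minute reading. If not, it gives no count.

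**Working it through.** The documents state no figure for this endpoint, so there is none to reproduce.

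**1. Can another rule give a non-reacher a time?** LOCF is confined to the efficacy analyses. Extrapolation, even read broadly, fills only points after the last observed value. A non-reacher with readings to 90 minutes has nothing to fill. No other rule applies.

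**2. Shift of the median, with no times assumed.** With N analysed subjects and r non-reachers, the reachers-only median sits at rank (N − r + 1)/2 among all N, against (N + 1)/2 when non-reachers are ranked last. The difference is r/2.

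| Non-reachers r | 0 | 1 | 2 | 3 |
|---|---|---|---|---|
| Rank, N = 6 | 3.5 | 3.0 | 2.5 | 2.0 |
| Rank, N = 12 (maximum per group, SAP 1.3) | 6.5 | 6.0 | 5.5 | 5.0 |

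**3. Illustration in minutes (assumed times).** Take six times of 15, 20, 25, 30, 35 and 40 minutes, with the slowest r subjects not reaching the rise and censored at 90 minutes.

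| Non-reachers r | 0 | 1 | 2 | 3 |
|---|---|---|---|---|
| Reachers-only median (the mean is the same) | 27.5 | 25.0 | 22.5 | 20.0 |
| Kaplan-Meier median | 27.5 | 27.5 | 27.5 | not reached |

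The Kaplan-Meier curve is 5/6, 4/6 and 3/6 after 15, 20 and 25 minutes. It equals 0.5 from 25 to 30 minutes, and the midpoint is 27.5. With r = 3 it stays at 0.5 and never falls below. One non-reacher makes the reachers-only median 2.5 minutes faster; two make it 5.0 minutes faster, which is one sampling step.

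**4. The half-censored exclusion.** Readings every 5 minutes from 5 to 90 (Protocol Table 4) give 18 post-dose values, or 20 with −5 and 0. Suppose the rise is seen at 20 minutes and an intervention falls between the 35- and 40-minute readings. Readings at 40 to 90 are censored: (90 − 40)/5 + 1 = 11. Then 11/18 = 61% and 11/20 = 55%. Both exceed half, so the subject and the observed 20-minute rise are removed.

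The SAP does not say which values form the denominator. With 18, exclusion needs at least 10 censored values, so a subject read through 40 minutes is still excluded. With 20 it needs at least 11, so the limit is 35 minutes.

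**5. Direction of that effect.** With the times in step 3, all reaching, removing the 20-minute riser leaves 15, 25, 30, 35, 40: median 30, which is 2.5 minutes slower than 27.5. Removing the 35-minute riser instead leaves 15, 20, 25, 30, 40: median 25, which is 2.5 minutes faster.

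**6. The 30-minute expectation, from the documents' own figures.** These come from healthy adults; normality is assumed.
- Mean 35, SD 18 (Protocol 13.1): 1 − Φ((25 − 35)/18) = 0.711, or 4.3 of 6 expected; all six, 0.711⁶ = 0.13.
- Mean 25, SD 18 (SAP 1.3): 1 − Φ(0) = 0.50, or 3.0 of 6; all six, 0.5⁶ = 0.016.

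These are shares at the single 30-minute reading. They show why a count is worth printing, but they do not estimate how many subjects never rise by 25 mg/dL within 90 minutes.

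**The case against.** The strongest reply is that the SAP nowhere says it will summarise reachers only. That is true: it is an inference from the observed-profile definition, the non-missing N and the absence of a rule. It still stands as the consequence of following the text, since no written instruction leads elsewhere.

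A reader might infer that the plan as a whole can only make the drug look faster. The documents do not support this. The direction holds among analysed subjects, but the exclusion in SAP 3.2 can remove a fast riser and slow the median (step 5), so the net effect is not determined.

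A reader might also take the 71% and 50% as success rates for this endpoint, or the minute shifts as expected errors. Neither is warranted. The shares concern one reading in healthy adults, later risers also obtain a time, and the minutes rest on assumed values.

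The exclusion is prespecified and aimed at interventions soon after dosing. Losing an observed rise requires a rise followed by an intervention. Protocol 10.2.1 allows intervention for distress at any time or for glucose below 70 mg/dL, so the sequence is possible. However, from a baseline of 70 to 79 the glucose limb would require a fall of more than 25 mg/dL after the rise. It may be rare.

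Finally, the shells print N for each column. Comparing the time N with the Cmax N exposes subjects without a time, and comparing the Cmax N with the Table 7 or 8 N exposes exclusions. This makes the problem partly visible but does not correct the mean or median.

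**Conclusion.** The point holds as a modest, inexpensive improvement to a descriptive secondary endpoint. The SAP has no rule for non-reachers. Followed as written, it drops them, and among analysed subjects each one lowers the median by half a rank. This needs no assumption about times, only the inference that a subject without a rise has no value.

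The exclusion of an already observed rise is a separate, arithmetically certain possibility under SAP 3.2. Its direction is open and its frequency is unknown. The primary endpoint and its t-test are not affected.

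**What to change.** In SAP 2.4.2, for time to a rise of at least 25 mg/dL only, and within the completed-visit cohort of SAP 3.2:

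- Do not apply the half-censored exclusion, and keep any rise observed before an intervention.
- Report n/N reaching the rise without intervention, by age group and dose.
- Report a Kaplan-Meier median over all included subjects. Censor non-reachers at their last reading, which also covers subjects whose later draws were dropped for blood volume (Protocol 11.1). Count a subject given an intervention before the rise as not reached, held at risk to 90 minutes. This matches the unaided rise in the primary objective (SAP 1.1.1). State the convention used when the curve equals 0.5.
- Keep the mean, SD and range that Protocol 13.2 prescribes, labelled as *among those reaching*.

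In SAP 3.2, keep the half-censored exclusion for AUC, Cmax and Tmax, and footnote the number excluded in Tables 9 and 10.

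The cost is a few sentences, a few table rows and a footnote, with no new data and no change to the cohort definition. The downside is that, with about six subjects, the median will be imprecise and may be *not reached*. When half or more of the subjects fail to reach the rise, that is the accurate answer.
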